5. STUDY INTERVENTIONS

5.1 Interventions, Administration, and Duration_

Specific recorded lullabies with simple arpeggiated accompaniment will be played for 6 weeks (+/- 1 week) in a small randomized, blinded, controlled study of 60 recruited medically stable 30 week preterms.

MBI subjects will receive a total of 1.5 hours of music intervention 4-5 sessions per week. Music will be alternating: 30 minutes on and 30 minutes off and will be played when the subject is awake to cue pacification and initiate the sleep process. Voice unaccompanied or with single accompanying

softly arpeggiated instrument is best for infants. Lullabies meet these criteria and promote language development due to an emphasis on vowels, rising and falling melodic phrases, and the recognition of soothing sounds. Lullabies will all have consistent tempos, with the melody in higher range sung by female or children as infants hear these pitches best. As it is recommended to change song order to increase stimulation, habituation, and neurological development, we will use 10 playlists. MP3 players will be loaded in advance with the entire 6 weeks of music. Within each week, order of the playlists will be randomly assigned and prepared in advance by [name]. MBI will have minimal interference with routine medical care.

5.2 Handling of Study Interventions

N/A

5.3 Concomitant Interventions_

N/A

5.4 Adherence Assessment

Adherence is defined as 80% compliance in this study – average of 4-5 intervention or control sessions per week. If adherence falls below 80%, the Internal QA Reviewer will discuss with the PI methods for improving adherence.

6. STUDY PROCEDURES

Assessment	Screen ing	Baseline/ Visit 1	2 weeks (+/- 3 days) Visit 2	4 weeks (+/- 3 days)	6 weeks (+/- 3 days) Visit 4	43-48 weeks corrected gestational age Visit 5/			
Informed Consent	x								
Randomization	x								
Demographics		x							
Medical History		x				x			
Physical Exam		x							
Vital Signs		x	x	x	x				
Baseline Lab Values		x							
Inclusions/Exclusion		x							
Concomitant Meds		x	x	x	x	x			
HADS*		x							
Music Exposure		x				x			
Baseline Checklist		x							
On Study Visit		x	x	x	x	x			
EEG		x	x	x	x				
PIPP		x	x	x					
ERP						x			
Adverse Events		x	x	x	x	x			
SAE		x	x	x	x	x			
Family Feedback**					X**				
Study Completion						x			

6.1 Schedule of Evaluations – Screening and Study Visits

**optional element (parent must provide specific consent to complete this assessment)*

** Family Feedback may be completed at any point before discharge from the hospital

6.1a Schedule of Evaluations – Music Based Intervention or Control Sessions

Assessment	1	2	3	4	5	6	7	8	9	10	11	12	13	14	15	16	17	18
Vital Signs	x	X	x	x	x	X	X	X	X	X	X	x	X	Х	Х	Х	Х	x
MBI Info Form	X	X	X	X	X	X	X	X	X	X	X	X	X	X	X	X	X	X
Assessment	19	20	21	22	23	24	25	26	27	28	29	30	31	32	33	34	35	36
Vital Signs	x	X	X	x	X	X	X	X	X	X	X	x	X	X	X	X	X	x
MBI Info Form	x	x	X	x	X	x	x	X	X	X	X	x	X	X	X	X	X	X

6.2 Description of Evaluations_

6.2.1 Screening Evaluation

Infants' medical histories will be screened to determine if infant is medically stable (no major organ system illnesses or sepsis) with no abnormal neurological exams, neonatal abstinence syndrome, intraventricular hemorrhage, seizures, meningitis, congenital brain malformations, or scalp lesions affecting the EEG application.

Consenting Procedure

The PI and other selected study investigators listed on the IRB will obtain a single informed consent that describes both the screening and study procedures. All study investigators who will be obtaining consent will receive training on how to determine eligibility of subjects and how to discuss the study with parents. The study investigator who obtains consent will ensure the parents understand the informed consent process and the requirements of the study.

The patient recruitment site will be the University of Minnesota Masonic Children's Hospital neonatal intensive care unit (NICU). Infants born at 30 weeks (+/- 2 weeks) who meet both inclusion and exclusion criteria will be identified by NICU staff. The neonatologist will first mention the study to the parent(s)/guardian(s), then ask whether they would be willing to further discuss the study with the study investigators. Study investigators include: (PI) [name], (Music Therapist) [name], [name], and the two study coordinators. The PI, [name], will oversee the consent process and make the final determination of the eligibility. Only parents/quardians who consent to hearing about the research study will be approached regarding enrollment of their infant. At the time of recruitment, all procedures, risks, benefits, and the option to withdraw from the study at any time will be explained to the parent(s)/guardian(s) of each participant and written, informed consent will be obtained. The voluntary nature of the study will be emphasized. The consent form will provide a description of the overall purpose of the research, the specific details of the protocol, risks and benefits, costs and payments, confidentiality, contact information for the PI, the posting of information on ClinicalTrials.gov, and the ability to withdraw from participation. At least one parent/guardian will sign the consent form on behalf of their infant. Assent will not be obtained because participants are not capable of providing it given their very young age (preterm newborn infants). A copy of the signed consent form will be kept in the study research files and medical records. The parent(s)/guardian(s) of participants will also be given a copy of their signed consent form. Parents will be informed that they can ask questions about the study at any time and contact information for the study staff will be provided on the consent form.

Process for meeting HHS regulatory requirements for parental permission and child assent

This study meets the requirements for 45 CFR 46.404 – Research not involving greater than minimal risk. Therefore, according to 45 CFR 46.408, the permission of one parent or guardian is sufficient for research to be conducted, pending IRB approval.

Screening

Both male and female potential subjects will be recruited from the patient population admitted to the University of Minnesota Masonic Children's Hospital NICU.

- Gestational age will be determined by mother's last menstrual period, fetal ultrasound measurements, and physical examination characteristics with a variability of +/- 14 days of the targeted 30 week gestational birth age for all subjects.
- Eligible infants must be medically stable (no major organ system illnesses or sepsis) with no abnormal neurological exams, neonatal abstinence syndrome, intraventricular hemorrhage, seizures, meningitis, congenital brain malformations, or scalp lesions affecting the EEG application.

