4.3 Study Enrollment Procedures_

Newborns will be recruited from the University of Minnesota Masonic Children's Hospital neonatal intensive care unit (NICU). We will ensure staff in the NICU are aware of the study and post flyers in the NICU to alert neonatology staff to the study's purpose, inclusion criteria, and the pager number needed to contact the study staff regarding potential subjects. The neonatologist will first mention the study to the parents, then ask whether the parents would be willing to further discuss the study with the study investigators. Only parents who express interest in learning about the research study will be approached regarding enrollment of their infant.

The PI and other selected study investigators listed on the IRB will obtain consent. All study investigators who will be obtaining consent will receive training on how to determine eligibility of subjects and how to discuss the study with parents. The study investigator who obtains consent will ensure the parents understand the informed consent process and the requirements of the study. Parents will be informed that they can ask questions about the study at any time and contact information for the study staff will be provided on the consent form.

Once eligibility has been confirmed and consent obtained, subjects will be randomly assigned to the MBI or control treatment cohorts in a 50:50 allocation ratio using randomization tables, stratified by sex and within each stratum use randomly allocated block sizes of 2 and 4, prepared by [name].

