6.2.3 Blinding

Blinding will be maintained by using identical headphones and MP3 players for all subjects. The PI, any personnel involved in collecting the clinical outcomes (e.g., PIPP) or collecting or quantifying EEG outcomes, and the statistician will be blinded. The statistician will be aware of blinded treatment group, so that e.g. safety summaries by blinded treatment group can be prepared for the Data Safety and Monitoring Board (DSMB) closed sessions if it so requests. Should the DSMB request unblinded comparisons, the study team will contract with the University of Minnesota CTSI's Biostatistical Design and Analysis Center (BDAC) for an independent statistician to work with the DSMB using unblinded data.

The unblinded staff includes [name] (music therapist) and [name] (Director of the NICU). [name] will prepare the music players. Both will be unblinded to handle randomization, delivery of interventions, and preparations of unblinded reports to the independent study monitors. They will not be involved with data monitoring, analyses, or outcome assessments.

The study coordinators who are assessing the PIPP will wear earplugs and noise cancelling headphones, which will ensure that s/he cannot hear what is emanating from the infant's headphones. In addition, family members and NICU staff will be reminded frequently to not disclose what they think they hear coming from the infant's headphones.

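### The unblinded music therapist is listed among those who discuss the study with parents, and the visible text neither keeps unblinded staff out of recruitment nor says how the randomization tables are concealed

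*Combined protocol and SAP*

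**What the plan says.** **Recruitment.** Under section 6.2.1, NICU staff identify eligible infants. The neonatologist mentions the study to the parents, "then ask whether they would be willing to further discuss the study with the study investigators". The same paragraph then says who these are: "Study investigators include: (PI) [name], (Music Therapist) [name], [name], and the two study coordinators". On consent, section 4.3 states: "The PI and other selected study investigators listed on the IRB will obtain consent". Sections 6.2.1 and 11.2 say much the same, and none of them names the selected investigators. Section 6.2.1 adds that the PI "will oversee the consent process and make the final determination of the eligibility".

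**Allocation.** Sections 6.2.3 and 9.2 name the music therapist and the Director of the NICU as unblinded staff. Of these two they say: "Both will be unblinded to handle randomization, delivery of interventions, and preparations of unblinded reports to the independent study monitors". The limit on their role follows: "They will not be involved with data monitoring, analyses, or outcome assessments". The PI, outcome collectors and statistician are blinded.

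**Mechanism.** Sections 4.3 and 9.2 use pre-prepared tables, 1:1, stratified by sex, with blocks of 2 and 4 in random order. The study statistician prepares them. Assignment follows consent and confirmed eligibility (4.3, 6.2.2, 9.2).

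**The concern.** Concealment of allocation and blinding of outcomes are separate safeguards. The plan's blinding measures (identical players and headphones, earplugs for PIPP assessors, reminders to staff and families) act after an infant has been assigned. They do nothing to stop knowledge of the sequence from influencing who enters the trial, or when.

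The music therapist is placed on both sides of that line: among the people parents are referred to, and among the people who know allocations. If someone in that position presents the study differently, or at a different time, according to the arm likely to come next, the two arms can differ before any music is played. Blinded scoring cannot undo that.

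The trial is small, with 60 infants recruited and 25 per arm expected with a 4-week PIPP. Section 9.5 compares arm averages with fixed milestone thresholds and describes no baseline adjustment, so an imbalance at entry would pass straight into the Go/NoGo figures that inform the R33 phase.

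**Working it through.** The plan gives no figure on this point to reproduce. The check sets the role statements side by side, then works out how predictable the sequence is.

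**Roles, by section**

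- Talks with parents: the PI, the music therapist, one other person and two coordinators (6.2.1).
- Takes consent: the PI and an unnamed subset of investigators (4.3, 6.2.1, 11.2). The music therapist is neither named nor excluded.
- Decides eligibility: the blinded PI (6.2.1).
- Handles randomization and delivers interventions unblinded: the music therapist and the NICU Director (6.2.3, 9.2).
- Closed to those two: data monitoring, analyses and outcome assessments (6.2.3, 9.2). Approaching families, consent and eligibility are not on that list.
- Concealment of the tables (sealed envelopes, central release, a holder outside recruitment): not described in the visible text.

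Delivering the intervention unblinded means knowing the assignments already made. Whether the next assignment is also known depends on how the table is held, which is not stated.

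**Predictability from past assignments alone**

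Inputs: 1:1 allocation and block sizes 2 and 4 within sex (4.3, 9.2). Assumptions not in the documents: the two block sizes are equally likely, and the person knows all past assignments in the stratum and always guesses the arm that is behind, tossing a coin when the arms are level.

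- Block of 2: the first guess is right with probability 0.5 and the second is certain. Expected correct = 0.5 + 1 = 1.5 of 2.
- Block of 4, first infant: 0.5.
- Block of 4, second infant: the arm that is behind has 2 of the 3 remaining places, so 2/3.
- Block of 4, third infant: the arms are level with probability 2/3 (guess right half the time), otherwise the rest is fixed. So 2/3 × 0.5 + 1/3 × 1 = 2/3.
- Block of 4, fourth infant: certain, 1.
- Block of 4, total: 0.5 + 0.667 + 0.667 + 1 = 2.83 of 4.
- Both sizes equally likely: (1.5 + 2.83) / (2 + 4) = 4.33 / 6 = 72%.

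Simulation with 30 infants per sex stratum (equal strata assumed) also gives 72.0%. If the chance of a block of 2 is 1/3 or 2/3 instead of 1/2, it gives 71.4% and 72.8%. The range is therefore about 71% to 73%, against 50% if past and future assignments are both hidden.

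**The case against.** The strongest reply is that the text shows an overlap of roles, not a breach. A reader might infer that allocation is known to someone who recruits, or that the therapist decides which family is approached and when. The documents support neither. No section says the music therapist takes consent, and none says the therapist sees an assignment before the infant is enrolled. Handling randomization could mean receiving each assignment after consent and setting up the player. NICU staff find the infants, the neonatologist opens the subject, only willing parents are approached, and a blinded PI makes the final decision on eligibility. That all stands, and it limits the risk to influence over a conversation with parents already prepared to listen.

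A reader might also suspect that the neonatologist who first raises the study is the unblinded NICU Director. Nothing says so, and the point does not rest on it.

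There is also limited room to choose. With 60% uptake, 60 infants imply 60 / 0.60 = 100 eligible infants over 18 months, or about 5.6 a month. And the order of steps is already right: assignment comes after consent and eligibility.

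That order does not settle the matter. Assigning after consent protects concealment only if the person in the conversation cannot predict the assignment, and past assignments in blocks of 2 and 4 are informative. The PI's decision applies only to families who reach that stage.

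Finally, the match between sections is by role because names are removed, and most of the study team roster is not in the text available here. A separation of duties written there cannot be ruled out.

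**Conclusion.** The concern holds as a gap in the separation of roles. Section 6.2.1 gives the music therapist a part in recruitment discussions, sections 6.2.3 and 9.2 give the same role knowledge of allocations, and no visible text separates the two or describes concealment of the tables. The existing gatekeeping reduces the risk without removing it.

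The only size that can be given is predictability: about 72% correct guesses from past assignments alone (71% to 73% over the block-size probabilities tried), resting on the guessing rule and full knowledge of past assignments in the stratum. It does not describe someone who can read the table. It is also not a measure of bias: how far any foreknowledge would move the PIPP cannot be derived from the documents, and a reader should not infer that the PIPP milestone is compromised. This is a cheap improvement to the plan, not evidence that enrolment was or will be steered.

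**What to change.** 1. In 6.2.1, remove the music therapist from the list of investigators who discuss the study with parents.
2. In 6.2.3 and 9.2, extend the exclusion sentence so that the unblinded staff also take no part, for the trial, in approaching or consenting families or in eligibility decisions.
3. In the same sections, state that each assignment is released to the unblinded staff only after consent and eligibility are recorded. The sequence is already in the plan; what has to be added is how the table is held until then.

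Sample size, outcomes and analysis do not change. The cost is protocol wording and one fewer person to talk with families. The blinded PI and the coordinators are already named for that task. If the roles are already separate in practice, the sponsor need only write that down.

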6.2.2 Enrollment, Baseline, and/or Randomization

Enrollment

All infants for whom a parent or legal guardian has signed consent will be considered to be enrolled in the study.

Baseline Assessments/ Visit 1

For participants who have successfully been screened for eligibility and are enrolled into the study, baseline assessments are performed. These include the following:

- Demographics
- Medical History
- Physical Exam
- Vital Signs
- Baseline Lab Values
- Concomitant Meds
- HADS (Hospital Anxiety and Depression Scale) for Moms
 - *optional element (mom must provide specific consent to complete this assessment)
- Music Exposure during Pregnancy

- EEG
- PIPP
- Adverse Events
- SAE

Randomization

Once eligibility has been confirmed and consent obtained, subjects will be randomly assigned to the MBI or control treatment cohorts in a 50:50 allocation ratio using randomization tables, stratified by sex, prepared by [name]. Randomization will occur immediately after screening.

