Updated protocol to reflect that ERPs will be conducted between 43-48 weeks corrected gestational age. See pgs 10,11,15,16, 26, 30. No impact on analysis. This allows for better compliance with allowing for scheduling families with a new born child.

Version Number 7.0

Version Date: February 1, 2022

Pg 20: Updated Section 6.1 Schedule of Evaluations – Screening and Study Visits to remove the 48 hour time period for baseline/visit 1 activities to occur. This change is administrative only as it has no impact on study aims, analysis or safety.

Version Number 8.0

Version Date: March 8, 2022

Pg 20-21: *Updated Section 6.1 Schedule of Evaluations &* Pg 25: *Section 6.2.4 Follow up Visits: Visits 2-5* to move Family Feedback form completion at Visit 4, noting though that this may be completed at any time prior to discharge.

TABLE OF CONTENTS

Page
FULL PROTOCOL TITLE
1 R61 A1010/12-01 1
Tool Revision History
TABLE OF CONTENTS 7
STUDY TEAM ROSTER
PARTICIPATING STUDY SITES
PRÉCIS 13
1. STUDY OBJECTIVES 14
1.1 Primary Objective (1) 14
1.2 Primary Objective (2) 15

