MBI subjects will receive a total of 1.5 hours of music intervention averaged at 4-5 sessions per week (Figure 2). Music will be alternating: 30 minutes on and 30 minutes off and will be played when the subject is awake to cue pacification and initiate the sleep process. Voice unaccompanied or with single accompanying softly arpeggiated instrument⁶⁶ is best for infants. Lullabies meet these criteria and promote language development due to an emphasis on vowels, rising and falling melodic phrases, and the recognition of soothing sounds. Lullabies will all have consistent tempos, with the melody in higher range sung by female or children as infants hear these pitches best.66 As it is recommended to change song order to increase stimulation, habituation, and neurological development, we will use ten playlists. MP3 players will be loaded in advance with the entire 6 weeks

of music. Within each week, order of the playlists will be randomly assigned and prepared in advance by [name]. MBI will have minimal interference with routine medical care. Study coordinators will monitor for any distress from music: finger splay, grimace, vital sign disturbance, or persistent crying.⁶⁷ If crying lasts longer than 5 minutes, the intervention will be stopped for that day's session. Blinding will be maintained by using identical headphones and MP3 players for all subjects. Headphones will be placed on each side of infant's head such that sound stimuli are received binaurally.⁶⁶ Music amplitude will be no more than 70 dB on Scale C.^{15,66,68}

Daily electronic volume level checks will avoid the need for listening checks of the headphones. Headphones will be placed 1 cm away from the ears to avoid discomfort from headphone compression. The headphones will either play music or silence for the control group.

Figure 4: Every two weeks, 30 hour EEG* recordings will capture two sessions of background frequencies and changes that occur with Session 1) MBI or Control intervention or Session 2) [MBI + pain] or [Control + pain]

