9.6 Missing Data

With regards to missing data, the built-in loss rate of 17% includes loss of subjects and also loss due to missing data. Thus, with our recruitment of 60 subjects, we should still be able to reach our 50 subject target completing PIPP data at 4 weeks of MBI.

This pilot clinical trial in the R61 phase is sufficiently small in sample size that imputation methods (e.g., missing week 4 PIPP value or sleep duration) are likely to perform poorly, specifically are likely to add substantial noise to the quantification of the Go/NoGo outcomes. The Go/NoGo quantifications will be computed without imputation and compared to the declared thresholds. Detailed infant and maternal characteristics from baseline assessments will be able to well describe the characteristics of those infants with missing data compared to those with complete data.

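### The plan does not secure a PIPP, sleep or EEG value before the first MBI/control session, yet it counts the 30-week values toward the Go milestones

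*Combined protocol and SAP*

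**What the plan says.** **Order.** Section 6.2.2: "Randomization will occur immediately after screening". The schedule table in section 6 marks randomization in the screening column. EEG and PIPP first appear in the Baseline/Visit 1 column.

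**Window.** The table gives later visits a tolerance, for example "2 weeks (+/- 3 days) Visit 2", and gives Visit 1 none. The revision history for version 7.0 agrees with this; its purpose was "to remove the 48 hour time period for baseline/visit 1 activities to occur".

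**Content of the recordings.** The Figure 4 legend in section 3 says: "Every two weeks, 30 hour EEG* recordings will capture two sessions of background frequencies and changes that occur with" either the assigned intervention alone or, in the second session, "Session 2) [MBI + pain] or [Control + pain". Visit 1 is neither named nor exempted.

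**Analysis.** Section 9.5 takes sleep at 30, 32, 34 and 36 weeks, and PIPP and lance-evoked EEG at 30, 32 and 34 weeks. It compares arms on these measures, and success at any single timepoint reaches the milestone. For PIPP the threshold is a mean at least 1 point lower under MBI. These series match the visits at which the schedule marks each assessment, so 30 weeks corresponds to Visit 1. Section 9.2 names PIPP at 4 weeks as the primary outcome. No section adjusts for an earlier value of the outcome.

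**The concern.** Visit 1 is called a baseline in sections 6.1 and 6.2.2 and used as an outcome timepoint in section 9.5. It cannot serve as both, and the text does not settle which it is.

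- If the Visit 1 EEG and lance are done under the assigned sound, the values may already carry a treatment effect. Section 2.1a promises serial trends and separates immediate from lasting effects, and those trends would then have no untreated starting point. Adjusting later values for Visit 1 would remove part of the effect.
- If they are done before the first session, any arm difference at 30 weeks is chance, and section 9.5 still accepts it as grounds for Go.

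The trial also forgoes a gain in precision. With about 50 infants expected at week 4, adjusting for the infant's own pre-session value is one of the few ways to sharpen the contrast without enrolling more.

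**Working it through.** **1. The plan's own figure.** Inputs from section 9.2: 25 per arm, SD 3.6, alpha 0.05. A two-sided two-sample t-test (48 degrees of freedom, noncentral t) gives a detectable difference of 2.91 at 80% power and 3.11 at 85%. The plan states 2.9 and 3.1. These figures reproduce and do not depend on a baseline, so there is no arithmetic error.

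**2. Chance of meeting the PIPP milestone with no true effect.** Assumptions: normal means, 25 per arm and SD 3.6 at every timepoint.

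- Standard error of the arm difference: 3.6 × √(2/25) = 1.018.
- One timepoint: P(difference ≤ −1) = P(Z ≤ −1/1.018) = P(Z ≤ −0.982) = 0.163.
- Independent timepoints: two give 1 − (1 − 0.163)² = 0.30; three give 1 − (1 − 0.163)³ = 0.41.
- Correlated timepoints, by simulation (the correlation is assumed, since the documents give none):

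| Correlation between timepoints | 32 and 34 weeks only | 30, 32 and 34 weeks |
|---|---|---|
| 0 | 30% | 41% |
| 0.3 | 28% | 37% |
| 0.5 | 26% | 33% |
| 0.7 | 24% | 29% |

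If Visit 1 precedes the first session, the gap between the columns (5 to 11 percentage points) is what counting it adds.

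**3. Gain from a pre-session covariate.** Let r be the correlation between pre-session PIPP and week-4 PIPP (assumed). The residual SD is 3.6 × √(1 − r²), with 47 degrees of freedom.

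| r | Residual SD | Detectable difference, 80% power | Power at 2.9 |
|---|---|---|---|
| none used | 3.60 | 2.91 | 80% |
| 0.3 | 3.43 | 2.78 | 83% |
| 0.5 | 3.12 | 2.52 | 90% |
| 0.6 | 2.88 | 2.33 | 94% |

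**4. Cost of adjusting for a treated Visit 1.** Let f be the share of the week-4 effect already present at Visit 1. The adjusted estimate targets 2.9 × (1 − r × f).

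- f = 0.5, r = 0.3: 2.9 × 0.85 = 2.465, power 70%.
- f = 0.5, r = 0.5: 2.9 × 0.75 = 2.175, power 68%.
- f = 1, r = 0.5: 2.9 × 0.50 = 1.45, power 36%.

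The last two fall below the 80% of an unadjusted analysis, as does the first, so a Visit 1 value taken under the assigned sound should not be a covariate.

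**The case against.** **The order is unstated, which is weaker than wrong.** A reader might infer that nothing is measured before treatment, so that Visit 1 is already treated. The documents do not support that. No text times the first session against Visit 1, section 6.2.2 calls the assessments baseline, and Figure 4 is a general legend that does not name Visit 1. The figures and the study diagram are not in the text available here, and a diagram could show the order. This objection stands. What remains is that the written plan gives no assurance.

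**The EEG probably contains sound-free hours.** The recording runs 30 hours, a session delivers 1.5 hours of music, and Measure 4 subtracts a resting state. This stands in part: the hours exist, but nothing says that any of them precede the first session.

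**Randomizing before baseline is acceptable.** It is, provided that measurement precedes the first session. Demographics, medical history and laboratory values are also collected, so only imbalance in the outcomes themselves is hidden. The unadjusted randomized comparison remains unbiased.

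**The trial is exploratory and Go/NoGo uses fixed thresholds, with no outcome adjustment planned.** So the power gain is an improvement and repairs no error, and step 4 warns against a misuse that nobody has proposed. The chance-pass calculation, however, concerns the thresholds directly.

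**The sponsor wants effects at different stages of prematurity.** The revision history says so, and an on-sound 30-week lance serves that aim. This is a real reason to keep it, but the value then cannot also be a baseline.

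**Conclusion.** The point holds as a gap and an inconsistency. The plan does not ensure that any PIPP, sleep or EEG outcome is recorded before the first session, and it treats the 30-week values as evidence of effect whichever way Visit 1 is run.

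If Visit 1 is pre-session, counting it raises the chance of a false PIPP pass from 24-30% to 29-41%. This rests on normality, 25 per arm, a common SD of 3.6 and an assumed correlation of 0-0.7. If Visit 1 is under the assigned sound, no baseline is secured, and the trial forgoes a fall in the detectable difference from 2.91 to 2.78-2.33 for an assumed r of 0.3-0.6.

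A reader might also infer that exposure at week 4 drifts by 4-5 sessions for each week between the first session and Visit 1. The documents show no such gap, and section 9.6 ("we should still be able to reach our 50 subject target completing PIPP data at 4 weeks of MBI") can be read as counting from the start of the intervention. That inference is not part of this conclusion.

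**What to change.** 1. Reconcile the Figure 4 legend in section 3, the schedule table, section 6.2.2 and section 9.5 on what Visit 1 is.
2. In sections 6.1 and 6.2.2, state that a Visit 1 EEG block covering sleep and rest is recorded before the first MBI/control session in both arms, using the early hours of the same 30-hour recording. State that the Visit 1 PIPP is scored before the first session where a standard-of-care lance allows.
3. In section 9.5, use these pre-session values as covariates for the later contrasts in Measures 1, 3 and 4, and do not count them toward any milestone.
4. If the 30-week lance stays under the assigned sound, say so and do not use its PIPP or evoked EEG as a covariate.

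**Cost.** No assessment is added, and for EEG the change is mainly one of wording. For PIPP there is a real trade-off. The on-sound lance at 30 weeks is given up, leaving those at 32 and 34 weeks. Because the study does not schedule lances, some Visit 1 PIPPs may be missed or some first sessions delayed. In return, the trial would also estimate the correlation between baseline and week 4, which is useful for planning the R33 phase.
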